## Methods/Design

### Trial design

The study is set up as cross-sectional observation of gait under four conditions, which follows a randomized sequence in order to avoid carry over effects. Chronologically, the assessments will start with the tertiary observation, investigating agreements between declined/inclined ramp and treadmill walking. Thereafter, three out of four conditions (self-paced walking, self-paced walking with internal focus of attention, and self-paced walking with real-time feedback) are tested under block randomization of their six possible permutations (ABC, BCA, CAB, CBA, ACB, BAC). With three conditions ( $n=3$ ), this represents the smallest number of permutations, equaling a Williams design, where each condition precedes each other condition equally often and each treatment occurs equally

frequently at each position. The fourth corresponding condition (speed-matched walking), can technically not take place before the corresponding real-time feedback condition, and is therefore exempted from the sequence randomization and always follows after self-paced walking with real-time feedback. Numbers of participants assessed for eligibility, allocated to assessments, and analyzed will be recorded by a modified CONSORT flow chart, without consideration of losses to follow-up, due the cross-sectional study design. Figure 1 illustrates a flowchart of the trial design.

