## **Short summary**

Control of the dynamic functional leg alignment (dFLA) and biomechanical load are important joint related aspects regarding the development of osteoarthritis (OA). Research on level walking with feedback on load related parameters provided innovative treatment possibilities. Concerning walking on sloped surfaces, fundamental biomechanical knowledge exists. However, deeper insights into the control of the dFLA during decline walking, and the usefulness of real-time feedback are missing. This study is set up as cross-sectional observation of gait under four conditions, which follows a randomized sequence in order to avoid carry over effects. Thirty (30) participants aged between 18 and 35 years will be included. They will complete a three-dimensional gait analysis on a 5-m ramp with 10° inclination. Afterwards they will be observed under four different conditions a) self-paced walking b) self-paced walking with internal focus of

attention, c) self-paced walking with real-time feedback, and d) condition c speed-matched walking, on a 10° declined split belt treadmill. The primary outcome parameter will be the frontal knee range of motion (fKROM). Secondary outcomes include the ground reaction force loading rate, spatial-temporal parameters, sagittal frontal and transversal kinematics, and kinetics for the lower extremities.

The findings should improve the understanding of effects of real-time feedback on the control of the dFLA and lower limb loading. Results will be published in a peer-review journal.

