## Study goals and objectives

This cross-sectional observation of decline walking under four conditions, aims at enhancing the understanding of the effects of real-time feedback on lower limb gait kinematics and kinetics. Furthermore, the agreement of kinematic and kinetic parameters of 10° decline and incline walking between ramp and treadmill will be assessed.

The primary research question is, whether real-time feedback alters the frontal knee range of motion when compared to self-paced walking on the one hand, and matched speed walking on the other hand. The secondary aspect focuses on the effect of lower limb loading in decline walking. Thirdly, parameters of interest will be compared between declined/inclined ramp and declined/inclined treadmill walking. Consequently, underlying hypotheses were phrased as follows:

Primary null hypothesis: Means of the outcome "frontal knee range of motion" are equal across the four conditions a) self-paced walking, b) self-paced walking with internal focus of attention, c) self-paced walking with real-time feedback, and d) condition c speed-matched walking. Predefined contrasts hypothesize that:

- 1) The outcome of self-paced walking with internal focus of attention and self-paced walking with real-time feedback is equal to speed matched walking ( $bc=d$ )
- 2) The outcome of self-paced walking with internal focus of attention and self-paced walking with real-time feedback is equal to self-paced walking ( $bc=a$ )
- 3) The outcome of self-paced walking with real-time feedback is equal to self-paced walking with internal focus of attention ( $c=b$ )

Primary alternative hypothesis: Means of the outcome "frontal knee range of motion" are NOT equal across the four conditions a) self-paced walking, b) self-paced walking with internal focus of attention, c) self-paced walking with real-time feedback, and d) condition c speed-matched walking. Two-sided testing will be applied, as knowledge from existing literature is only moderate. Predefined contrasts hypothesize that:

- 1) The outcome of self-paced walking with internal focus of attention and self-paced walking with real-time feedback is NOT equal to speed matched walking ( $bc \neq d$ )
- 2) The outcome of self-paced walking with internal focus of attention and self-paced walking with real-time feedback is NOT equal to self-paced walking ( $bc \neq a$ )

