## Recruitment, informed consent and randomization

Students and staff of the FH Campus Wien – University of Applied Sciences will be addressed with the study information via in-house corridor monitors and an email newsletter. If interested, they may contact the primary investigator. A research team member will check eligibility and provide study details. An assessment date will be agreed in case of willingness and eligibility of the potential participant. Written informed consent will be obtained from the participants prior to the assessments. The participants will randomly be assigned to one of the three sequences, by means of a prepared sequence list as derived from a random sequence generator online tool. Due to the nature of the studied conditions, it will neither be possible to conceal the allocation, nor to blind participants or researchers. A participant will pass through all assessments within one day. Shopping vouchers of 30 € will be offered as incentive for participation.

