## Examination Procedures

At first, height will be measured with a stadiometer to the nearest 0.5 cm (SECA 213), and weight with a medical scale (Marsden M-420). Furthermore, joint range of motion and functional hamstring flexibility will be assessed. Thereafter, all participants will be equipped with 43 retroreflective markers on bony landmarks and 16 markers on four rigid clusters on thighs and shanks. Five level walking trials will be captured to evaluate if gait pattern is physiological or not. Participants will have to walk on a five-meter ramp with 10° inclination which is equipped with 24 infrared cameras (Vicon, Oxford, United Kingdom) and two force plates (Kistler, Winterthur, Switzerland). After seven left and seven right foot strikes on

the force plates for up and down walking each, the participants will be guided to the Gait Real-time Analysis Interactive Lab (GRAIL, Motekforce Link, Amsterdam, Netherlands), which is located next door. The GRAIL is a dual-belt treadmill equipped with two force plates, a 180° virtual reality screen and a motion capturing system with ten infrared cameras. After the familiarization phase on the treadmill with an inclination of 10° and with matched speed of incline walking, three times a period of 20 seconds will be recorded within 3 minutes. The investigator will explain the self-paced mode of the treadmill to the participant afterwards. The self-paced mode will adapt the belt speed automatically based on the position of the participant on the treadmill. Following a familiarization phase, data will be recorded as before.

This procedure will be repeated on the treadmill with a declination of 10°. Thereafter, the three following tasks will be performed in the order as specified in the sequence list.

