#### *Self-paced decline walking*

The participants will be instructed to walk on the declined treadmill with self-selected speed. They will complete a five-minute familiarization period and a three-minute measurement period. Within the measurement phases, three times a period of 20 seconds of self-paced walking will be recorded.

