#### *Self-paced decline walking with real-time feedback, followed by speed-matched decline walking*

The participants will be instructed to walk on the declined treadmill with self-selected speed. During walking, they will have to concentrate on specific real-time feedback presented on the projection screen. This feedback visualization will represent the simplified frontal knee alignment movement using the participants knee position in relation to the ankle. The participants will complete a five-minute familiarization period and a three-minute measurement period. In the measurement phases, three times a period of 20 seconds of self-paced walking will be recorded. After this task, a control trial will take place with matched speed and without any feedback instruction.

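### Speed-matched walking always directly follows feedback, so feedback carry-over cannot be separated from contrast 1, although the plan says the randomised sequence avoids carry-over

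*Combined protocol and SAP*

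**What the plan says.** The combined protocol and SAP describes the study in the Short summary as a "cross-sectional observation of gait under four conditions, which follows a randomized sequence in order to avoid carry over effects", and the opening of Trial design repeats this. Trial design then limits the randomisation to three conditions: a (self-paced), b (internal focus) and c (real-time feedback). These are block-randomised over six permutations, and Williams balance is claimed for those three. Condition d "is therefore exempted from the sequence randomization and always follows after self-paced walking with real-time feedback", because its speed is not known until c has been walked.

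The examination section places d straight after the feedback task: "After this task, a control trial will take place with matched speed and without any feedback instruction". No washout is described. For a, "They will complete a five-minute familiarization period and a three-minute measurement period", and b and c have the same timings; no duration is given for d.

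The primary question asks whether feedback changes frontal knee range of motion "when compared to self-paced walking on the one hand, and matched speed walking on the other hand". Contrast 1 sets b and c together against d, and the same contrasts apply to loading rate. Statistical analysis plans a one-factor repeated-measures ANOVA with contrasts and mentions no term for order, time or carry-over. The limitations section notes that d is outside the randomisation and goes no further. On the number of sequences, Recruitment, informed consent and randomization says: "The participants will randomly be assigned to one of the three sequences".

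**The concern.** The plan gives its randomised sequence the job of preventing carry-over, but for d the sequence cannot do that job. If walking with feedback changes how a person walks for some minutes afterwards, d is recorded while that change is still present. The matched-speed comparison would then be pulled towards zero, or past it, by the very effect under study. A null contrast 1 could be reported as feedback making no difference at equal speed when it reflects persistence. The reader is not warned.

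Putting d after c also disturbs the balance of the other conditions over time. Fatigue or continued adaptation to the sloped treadmill could then enter all three contrasts, because the model has nothing to absorb it.

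**Working it through.** **Inputs from the documents.** Six permutations of a, b, c, with d inserted directly after c (Trial design; feedback task description); 5 + 3 = 8 minutes for each of a, b and c (task descriptions); 30 recruited (Sample size estimation); two-sided alpha 0.05 (Statistical analysis). **Assumed, because not given:** the length L of d, the drift t per 8-minute task, the share k of the feedback effect f that persists, no effect of b, equal numbers per sequence, and recording at the end of each task.

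**The plan's own claim.** Over ABC, BCA, CAB, CBA, ACB, BAC each condition takes each position twice, and each ordered neighbour pair occurs twice. The balance claimed for three conditions is correct.

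**After inserting d.** The orders become ABCD, BCDA, CDAB, CDBA, ACDB, BACD.

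| Condition | Times in slot 1, 2, 3, 4 | Mean slot |
|---|---|---|
| a | 2, 1, 1, 2 | 2.5 |
| b | 2, 1, 1, 2 | 2.5 |
| c | 2, 2, 2, 0 | 2.0 |
| d | 0, 2, 2, 2 | 3.0 |

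d is preceded by c in 6 of 6 orders, and c never directly precedes a or b.

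**Carry-over: estimability.** An indicator for being preceded by c equals the indicator for d, row for row. With 30 participants, adding it to a model with person, condition and slot gives rank 36 for 37 columns. bc-d is then not estimable; c-b and bc-a still are. This needs no assumed effect size, drift or task length.

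**Carry-over: size.** Feedback precedes b in 3 of 6 orders (CDAB, CDBA, ACDB) and a in 3 of 6 (BCDA, CDAB, CDBA).
- Persistence into d only: c = f, b = 0, d = kf, so bc-d = 0.5f - kf = (0.5-k)f, which is zero at k = 0.5.
- Persistence through all later tasks: mean b = 0.5kf, so bc-d = 0.5(f + 0.5kf) - kf = (0.5-0.75k)f, which is zero at k = 0.67.
- In the second case the other contrasts also shrink: c-b = f - 0.5kf = (1-0.5k)f, and bc-a = 0.5f + 0.25kf - 0.5kf = (0.5-0.25k)f.

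**Drift.** With L = 8, bias follows from the mean slots:
- bc-d: (2.5 + 2.0)/2 - 3.0 = -0.75t
- c-b: 2.0 - 2.5 = -0.50t
- bc-a: 2.25 - 2.5 = -0.25t

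Each is multiplied by L/8 when d is shorter, so bc-d is -0.375t at 4 minutes and -0.28t at 3 minutes.

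**Illustrative false-positive rates.** Simulated for the unadjusted bc-d test, n = 30, nominal 5%:

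| Length of d | t = 0.1 SD | t = 0.2 SD | t = 0.3 SD |
|---|---|---|---|
| 8 min | 6% | 9% | 15% |
| 4 min | 5% | 6% | 7% |
| 3 min | 5% | 5% | 6% |

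(SD is the within-person residual SD.)

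**Effect of adjusting for elapsed time.** Linear-drift bias becomes 0 at every L. The variance of bc-d times n goes from 1.500 to 1.625 (L = 8) or 1.525 (L = 3). The standard error therefore rises by sqrt(1.625/1.500) - 1 = 4.1%, or sqrt(1.525/1.500) - 1 = 0.8%. If instead only the first slot differs, by s, and L = 8, the adjustment moves bc-d from +0.33s to +0.11s but c-b from 0 to -0.15s.

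**Three sequences.** Recruitment does not name them. If they are one of the two cyclic sets (ABC, BCA, CAB or CBA, ACB, BAC) and L = 8, the biases are -0.83t or -0.67t (bc-d), -0.33t or -0.67t (c-b) and -0.50t or 0 (bc-a).

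**The case against.** The strongest reply is that the plan already discloses the design. Trial design says that only three of the four conditions are randomised, claims balance for three only, explains why d must follow c, and the limitations section repeats that d is not randomised. This stands as far as it goes. A reader might infer that the fixed order was concealed or that d ought to have been randomised; the documents support neither. What they omit is the consequence for contrast 1, and the four-condition claim about carry-over still opens Trial design and stands in the Short summary.

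A second reply is that drift may be negligible. Participants have already walked on the declined treadmill at matched and self-paced speed before these tasks, and a, b and c each include five minutes of familiarisation. If d lasts only 3 or 4 minutes, the illustrated error rates barely leave 5%. This also stands. A reader might infer that the primary test has a 15% error rate; that figure needs both an 8-minute d and an assumed drift of 0.3 SD, neither of which is in the documents.

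Third, a time adjustment is no cure. It cannot touch carry-over, it removes only linear drift, and it can shift c-b under other shapes. That is right, and is why it belongs in a sensitivity analysis and not in place of the planned ANOVA.

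**Conclusion.** The point holds, with carry-over as the main part. That bc-d cannot be separated from feedback carry-over is a property of the order and rests on no assumption; a direct comparison of c with d has the same weakness. How far carry-over distorts the result is unknown: the break-even share is 0.5 or 0.67 depending on how long persistence lasts, and the documents give no value for it. The finding does not show that carry-over occurs or that contrast 1 is useless. It shows that a null contrast 1 is not evidence that feedback has no effect.

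A reader might also infer that carry-over is avoided among a, b and c. It is not: randomising their order balances feedback carry-over between a and b, but does not remove it.

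Drift is secondary. The biases of -0.75t, -0.50t and -0.25t assume linear drift, six equally used sequences and an 8-minute d, and fall in proportion to the length of d.

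**What to change.** 1. In the Short summary and Trial design, replace the carry-over claim with a statement that randomising a, b and c balances order over those three conditions, does not remove carry-over, and does not protect d.
2. In Statistical analysis and in the limitations section, state that carry-over from feedback into d cannot be removed by analysis, that bc-d compares with walking recorded immediately after feedback, and that a null bc-d does not show absence of a feedback effect. Give both persistence expressions.
3. State how long d lasts. Keep the planned ANOVA as primary and pre-specify one sensitivity analysis of the three contrasts, for frontal knee range of motion and loading rate. Adjust it for the mean elapsed walking time of the recordings that are averaged in each condition, which matches the single averaged value per condition in Outcome parameters. Use an unstructured within-person covariance or contrast-specific errors.
4. Reconcile six sequences (Trial design) with three (Recruitment) and state which list is used, because the drift bias depends on it.

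The cost is wording plus one extra model, with no added participants or measurements. Recording times must be available or derivable from the sequence list and task durations. The adjusted bc-d has a standard error about 4% larger if d lasts 8 minutes and under 1% larger if it lasts 3. Any difference between the adjusted and planned results should be read knowing that the adjustment handles linear drift only and may itself shift c-b.

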**Figure: Flow diagram of the progress through the phases of the trial**

## Sample size estimation and study population

As knowledge and studies concerning the effect of real-time feedback during decline walking is missing, sample size calculation based on proven effects is not applicable. Therefore sample size was arbitrary estimated with 25 based on the number of participants included in topic-specific studies, ranging from 14 to 40. Taking into account a drop out of 20% we will recruit 30 participants.

Those healthy participants will be included, according to the following inclusion criteria: 1) age from 18-35 years, 2) body mass index from 18.5 to 29.99 kg/m^2, 3) no chronological joint diseases and/or OA surgery, and 4) no neuro-motor diseases. Participants will be excluded from the analysis in case of 1) non-physiological and non-symmetrical gait patterns, and 2) severe outliers (more than two standard deviations).

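### Do 30 recruits fall one short of the target of 25 once a 20% drop-out is allowed for?

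*Combined protocol and SAP*

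**What the plan says.** All the relevant figures are in the protocol section Sample size estimation and study population. It explains that, for want of earlier work on feedback during decline walking, "sample size calculation based on proven effects is not applicable". The target is therefore a matter of judgement: "sample size was arbitrary estimated with 25", chosen "based on the number of participants included in topic-specific studies, ranging from 14 to 40". The next sentence gives the recruitment figure: "Taking into account a drop out of 20% we will recruit 30 participants". It does not say what the 20% is a percentage of.

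The number 30 is repeated in the Short summary ("Thirty (30) participants aged between 18 and 35 years will be included"), and the study codes under Ethical and data protection aspects run from UD01 to UD30.

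Three further statements bear on how many will be analysed:

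- The sample size section removes some participants after measurement ("Participants will be excluded from the analysis in case of"), on grounds of gait pattern or of values more than two standard deviations out.
- Recruitment, informed consent and randomization has each participant complete everything within a single day.
- Trial design promises an account of the numbers: "Numbers of participants assessed for eligibility, allocated to assessments, and analyzed will be recorded by a modified CONSORT flow chart". It leaves out losses to follow-up because the design is cross-sectional.

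**The concern.** A drop-out rate is ordinarily quoted as a share of the people enrolled. Read that way, the plan recruits too few for its own target. Dividing by one minus the rate is the usual way to allow for loss, and multiplying by one plus the rate is a familiar slip that always gives a number that is too small. A reader who checks the sum in the usual way finds a mismatch and may suspect that the planned sample size will not be reached at the planned rate of loss.

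In a trial with a powered sample size, such a shortfall would take something from the stated power. Here it would mean analysing 24 people where 25 were intended.

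**Working it through.** **Inputs.** Target 25, drop-out 20%, recruits 30, all from Sample size estimation and study population. The 30 is confirmed in the Short summary and by the study codes. The protocol gives no effect size, standard deviation or power.

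**Reproducing the plan's figure.** Adding 20% of the target to the target: 25 × (1 + 0.20) = 30. This equals the stated number with no rounding.

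**The other reading.** Taking the 20% of those recruited:

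- completers expected from 30 recruits: 30 × (1 − 0.20) = 24, which is 25 − 24 = 1 below target;
- recruits needed for 25: 25 / (1 − 0.20) = 31.25, rounded up to 32, which is 32 − 30 = 2 more than planned.

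**The two allowances on one scale.** Keeping 25 of 30 permits a loss of 5, and 5 / 30 = 16.7% of recruits. A 20% loss of recruits is 6 of 30. The two readings differ by one person.

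**What one person is worth.** The protocol states no precision, so this is only an illustration. The half-width of a 95% confidence interval for a paired mean difference, in standard deviations of the differences, is t(0.975, n − 1) / √n:

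| n | half-width (SD of the differences) |
|---|---|
| 25 | 0.413 |
| 24 | 0.422 |

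The unrounded values are 0.4128 and 0.4223, and 0.4223 / 0.4128 = 1.023, so the interval is 2.3% wider with 24.

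**Against the basis of the target.** The comparable studies had between 14 and 40 participants. Both 24 and 25 lie well inside that range, so the argument for the target supports either number equally.

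**Allocation.** Trial design uses six orders of the three randomised conditions. Thirty recruits give 30 / 6 = 5 per order; 32 do not divide evenly by six. Recruiting two more to satisfy the stricter reading would therefore disturb the balance of orders, for the sake of one participant.

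**The case for a change.** The best case for acting is that the allowance is vague in more than its base. Assessments are finished in one day, so ordinary attrition should be small, and the margin may in practice be used up by the exclusions for gait pattern and outliers. The protocol does not say whether those exclusions count towards the 20%, nor which measures the two-standard-deviation rule covers.

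They could matter. If the data are normal and the rule is applied to one measure in one condition, about 4.6% of participants lie beyond two standard deviations, or about 1.4 of 30. If it is applied in four conditions that are taken as independent, the share is 1 − (1 − 0.0455)^4 = 17%, about 5 of 30; correlation between conditions would lower this. On this view one sentence that fixes the margin at 5 and counts the exclusions within it would cost nothing.

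Part of this stands. The base is unstated, and the number removed by the outlier rule is uncertain and could take up anything from a small part to all of the allowance. But that uncertainty comes from the exclusion rule, and naming the denominator of the 20% does nothing to reduce it. Counting the exclusions within the drop-out would also add a rule that the protocol does not contain. It is a separate matter and should not be settled as a by-product of a wording point.

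The single-day design also weakens the premise of the objection. With no follow-up period, a percentage added on top of the target is a natural way to express a reserve, and the protocol's own numbers fit that use.

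**Conclusion.** No change is needed. The protocol leaves the base of a percentage unstated, but the calculation does not fail. Adding 20% to the target gives the recruitment number exactly, and no other section conflicts with that reading. The shortfall appears only under a convention which the protocol does not adopt and which its figures do not fit.

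Even on the stricter reading the difference is one participant analysed, or two recruited. The target it is measured against rests on no power calculation, so no stated property of the trial is lost. Thirty people are recruited in either case and the analysis is the same. The flow chart will show how many were allocated and how many analysed, so the actual loss will be visible whatever the 20% was meant to describe.

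This conclusion assumes that the 20% was meant as an addition to the target. The protocol does not say so, and the inference rests on the exact agreement of the three figures. If the assumption is wrong, the consequence is still no more than the one participant described above.
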